#### 7.1.2 Adverse Reaction

Adverse reactions are a subset of all suspected adverse events for which there is reason to conclude that the drug caused the event. Suspected adverse reaction means any adverse event for which there is a reasonable possibility that the drug caused the adverse event. For the purposes of safety reporting, "reasonable possibility" means there is evidence to suggest a causal

relationship between the drug and the adverse event. A suspected adverse reaction implies a lesser degree of certainty about causality than an adverse reaction, which means any adverse event caused by a drug. Examples of evidence that suggest a causal relationship (reasonable possibility) between the drug and the adverse event include:

- A single occurrence of an event that is uncommon and known to be strongly associated with drug exposure
- One or more occurrences of an event that is not commonly associated with drug exposure, but is otherwise uncommon in the populations exposed to the drug
- An aggregate analysis of specific events observed in a clinical trial (such as known consequences of the underlying disease or condition under investigation or other events that commonly occur in the study population independent of drug therapy) that indicates those events occur more frequently in the drug treatment group than in a concurrent or historical control group.

#### 7.1.3 Serious Adverse Event/Reaction

A serious adverse event (SAE) or reaction is defined as "any adverse event occurring at any dose that suggests a significant hazard, contraindication, side effect, or precaution." An adverse event or suspected adverse reaction is considered "serious" if, in the view of either the investigator or sponsor, it results in any of the following outcomes:

- Death. A death that occurs during the study or that comes to the attention of the investigator during the protocol-defined follow-up after the completion of therapy must be reported whether it is considered to be treatment related or not.
- 2. A life-threatening adverse event. A life-threatening event is any adverse therapy experience that, in the view of the investigator, places the participant at immediate risk of death from the reaction as it occurred.
- Hospitalization or prolongation of existing hospitalization with the exception of hospitalization relating to initial diagnosis of type 1 diabetes.
  - a) Note: In general, hospitalization signifies that the participant has been detained (usually involving at least an overnight stay) at the hospital or emergency ward for observation and/or treatment that would not have been appropriate in the physician's office or out-patient setting. Complications that occur during hospitalization are AEs. If a complication prolongs hospitalization or fulfils any other serious criteria, the AE is serious. When in doubt as to whether 'hospitalization' occurred or was necessary, the AE should be considered serious.
- Persistent or significant incapacity or substantial disruption of the ability to conduct normal life functions
- Congenital anomaly or birth defect.
- Important medical events that may not result in death, be life-threatening, or require hospitalization may be considered serious when, based upon appropriate medical judgment, they may jeopardize the patient or subject and may require medical or surgical intervention to prevent one of the outcomes listed above.

An adverse event or suspected adverse reaction is considered "life-threatening" if, in the view of either the investigator or sponsor, its occurrence places the patient or subject at immediate risk of death. It does not include an adverse event or suspected adverse reaction that, had it occurred in a more severe form, might have caused death.

Regardless of the relationship of the adverse event to study drug, the event must be reported as a serious adverse event if it meets any of the above definitions.

### 7.1.4 Unexpected Adverse Event

An adverse event/reaction is considered unexpected when the nature (specificity) or severity of the event is not consistent with the risks described in the Investigator's Brochure. This includes events that occur more frequently than expected.

# 7.1.5 Grading Event Severity and Causality

TrialNet has adopted usage of the National Cancer Institute (NCI) Common Technology Criteria for Adverse Events (CTCAE) and/or study-specific criteria for classification to describe the severity of adverse events. TrialNet Investigators will also provide an assessment of relationship of AE to study drug as not, unlikely, possibly, probably, or definitely related.

The CTCAE v5.0 displays Grades 1 through 5 with unique clinical descriptions of severity of each AE based on this general guideline:

- Grade 1: Mild; asymptomatic or mild symptoms; clinical or diagnostic observations only; intervention not indicated.
- Grade 2: Moderate; minimal, local or noninvasive intervention indicated; limiting age appropriate instrumental activities of daily living (ADL)
- Grade 3: Severe or medically significant but not immediately life-threatening; hospitalization or prolongation of hospitalization indicated; disabling; limiting ADL
- Grade 4: Life-threatening consequences; urgent intervention indicated
- · Grade 5: Death related to AE

A semicolon indicates "or" within the description of the grade

### 7.2 Adverse Event Reporting and Monitoring

Adverse events will be reported to the TrialNet Coordinating Center. The investigator will grade their severity according to common toxicity criteria or study-specific criteria and will make a determination of their relation to therapy. Events will be assessed and reported consistent with the ICH Guideline for Good Clinical Practice, 21 CFR 312.32 for expedited safety reporting, and per the guidance of the DHHS Office for Human Research Protections (OHRP).

The adverse event case report form for the protocol must be completed for all adverse events (AE). For all types of injection site reactions additional information about the objective findings and local symptoms must also be reported in the injection site reaction section of the case report form. For reporting serious adverse events (SAE), the MedWatch Form should also be completed and faxed to the TNCC within 24 hours of when the site was notified of the event. This will be reviewed by the TrialNet Medical Monitor, Novo Nordisk Trial Safety Group, and the DSMB as appropriate. Deaths must be reported immediately. Event outcome and other follow-up information regarding the treatment and resolution of the event will be obtained and reported when available, if not known at the time the event is initially reported. The follow-up information should contain sufficient detail to allow for a complete medical assessment of the case and an independent determination of possible causality.

Adverse events will be assessed by the TrialNet Medical Monitor. Formal safety evaluations will occur by TrialNet Medical Monitor, Novo Nordisk Trial Safety Group, and the DSMB as indicated

by enrolment and trial progress. Additional review will occur during regularly schedule DSMB meetings which occur approximately every six months.

For SAEs that are unexpected and considered possibly or probably drug related, the Medical Monitor will provide information on frequency of similar events, and generate FDA form 3500A reports (MedWatch form) for distribution to FDA, NIDDK, DSMB and site investigators. Expedited safety reports will be submitted to the IND by the NIDDK. The TNCC will also be responsible for sending required safety information to Novo Nordisk Safety.

#### 7.2.1 Adverse Event Tabulations

All reported adverse events will be tabulated by system organ class (SOC) (e.g., cardiac disorders, endocrine disorders, infections and infestations, etc.), supra-ordinate term (e.g., palpitations, hyperthyroidism, appendicitis, etc.), severity, expectedness (per the investigational brochure and causality in relation to the study agent. Adverse events are reported separately for the number of study participants and the number of events should study participants experience the same type of event multiple times.

# 8 STATISTICAL CONSIDERATIONS AND ANALYSIS PLAN).

The primary objective of this study is to investigate the safety and tolerability of ascending subcutaneous weekly doses of NNC0361-0041 plasmid in patients with T1D. Secondary objectives are to investigate effect on target engagement, immune response, and beta cell function following ascending subcutaneous weekly doses of NNC0361-0041 plasmid in patients with T1D.

Up to 12 patients will be randomized to treatment vs. placebo within each of the 4 cohorts. The goal is to have a minimum of 9 patients within each cohort to have received at least 10 of the planned 12 treatment doses.

The following groups and periods are defined for analytic purposes:

Randomized:	Met eligibility criteria and randomly assigned to a treatment arm without consideration of actually receiving treatment.
Randomized and partially treated:	Met eligibility criteria, randomly assigned to a treatment arm and received at least 1 – 9 doses.
Randomized and treated:	Met eligibility criteria, randomly assigned to a treatment arm and received at least 10 doses.
Pretreatment period	From signing of informed consent until 1st treatment
On-treatment period	From 1 st treatment through visit 15 (or 5 weeks after last treatment for subjects not receiving all injections)
Follow-up period	From visit 15 (or 5 weeks after last treatment) through visit 17

Up to 2 additional individuals within each cohort may be enrolled to complete the target 9 patients randomized and treated to account for those who are randomized and partially treated for any

reason, including COVID-19 vaccination. Additional individuals may be enrolled upon agreement between TrialNet and Novo Nordisk

All randomized subjects will be used for analyses of PK endpoints and all subjects receiving at least one dose of randomized treatment (partially treated and treated combined) will be used for analyses of the primary endpoint. Subjects receiving placebo treatment will be pooled across cohorts.

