#### 4.5 Infectious Disease Screening

In general, no specific infectious diseases prophylaxis is warranted in this study. In lieu of active serologic or virologic monitoring strategies, all subjects will be counseled on an ongoing basis on the importance of notifying their research centers about the presence of signs or symptoms suggestive of infection. They will also be counseled on the importance of notifying the research center about potential exposures to varicella, influenza, COVID-19 or other infectious illnesses.

Subjects will be assessed for COVID-19 symptoms at each study visit specified in the schedule of assessments. Subjects are required to be free of COVID-19 symptoms for 14 days prior to the screening visit, administration of study drug dose 1 and follow-up visits 15–17. For study drug administration of doses 2–12 and follow-up visit 14, participants are required to be free of COVID-19 symptoms the 7 days (or per current local guidance/CDC guidance) prior to those visits.

Subjects will not be enrolled with active infections, history of current or prior HIV, Hepatitis B, or Tb infection. In addition, all subjects will have CMV and EBV serology determined prior to study enrollment. Subjects who are CMV and/or EBV seronegative at screening must be CMV and/or EBV PCR negative within 30 days of randomization and may not have had signs or symptoms of an CMV and/or EBV compatible illness lasting longer than 7 days

within 30 days of randomization. Additional CMV and EBV seronegative individuals will have samples collected to be stored and tested for viral load if clinically indicated.

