### 5.5 Visit Windows

Enrollment and initial treatment visit (visit 0) should begin within 1 month (no more than 37 days) from the screening visit (visit -1). Dosing visits (visit #3-#13) should be within +/- 1 day from the

target date. Study visit 14 should be within -1/+1 day of the target date, visit 15 should be within -3/+3 days from the target date. The window for the 6- and 12- month time points (visits 16 and 17) is +/- 14 days.

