#### 7 ADVERSE EVENT REPORTING AND SAFETY MONITORING

#### 7.1 Adverse Event Definition

#### 7.1.1 Adverse Event

In this clinical trial, an adverse event is any occurrence or worsening of an undesirable or unintended sign, symptom or disease whether or not associated with the treatment and study procedures.

From study start through visit 15, the investigator must record all adverse events which are Grade 1 or greater per the NCI CTCAE (see Section 7.1.5. Grading Event Severity below), except for events related to hypoglycemia or hyperglycemia. Hypoglycemia and hyperglycemia should be recorded as adverse events only in the case of requiring the assistance of others due to loss of consciousness or DKA. After visit 15 only grade two or higher AEs are to be recorded (visits 16 & 17).

All SAEs must be recorded throughout the study (from signing of informed consent through visit 17).

The investigator should treat participants with adverse events appropriately and observe them at suitable intervals until the events resolve or stabilize.

Adverse events may be discovered through:

- observation of the participant;
- questioning the participant;
- unsolicited complaint by the participant.

Questioning of the participant should be conducted in an objective manner.

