### 8.1 Primary Outcome and Analyses

The primary endpoint is the number of adverse events recorded during the on-treatment period. The primary endpoint will be presented in a summary table including number of AEs, number of subjects with at least 1 AE and percentage of exposed subjects with at least 1 AE. A summary table will also be made by system organ class and trial product.

Serious adverse events will be summarized over the entire trial (i.e., on-treatment and follow-up period).

A statistical analysis plan will be written in addition to the protocol including a more detailed and technical elaboration of the statistical analyses. The statistical analysis plan will be finalized before unblinding (database lock).

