### 8.3 Additional Outcomes and Analyses

It is the aim to perform additional analysis to get information of the appearance and disappearance of Plasmid DNA and RNA at various time points during the trials conduct period:

- Plasmid DNA and RNA concentrations at selected time points before and from 1 hour to up to 48 hours after the first dose (Visits 0-2, days 0-2)
- Plasmid DNA and RNA concentrations before second dose (Visit 3, day 7 +/- 1 day)
- Plasmid DNA and RNA concentrations before dose 5 (Visit 6, day 28 +/- 1 day)
- Plasmid DNA and RNA concentrations before dose 8 (Visit 9, day 49 +/- 1 day)
- Plasmid DNA and RNA concentrations at selected time points after last dose (Visit 14, day 84 +/- 3 days; Visit 15, day 120 +/- 14 days; Visit 16, day 180 +/- 14 days; and Visit 17, day 365 +/- 14 days)

Additional analysis of the impact of study drug on metabolic outcomes (Section 5.4) will be determined at 1, 3, 6, and 12 months following treatment including analysis of changes of these parameters from baseline.

The impact of COVID-19 vaccination and response to vaccination on clinical and immune responses to study drug may be evaluated, as needed.

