6 ENDPOINTS AND COVARIATES

6.1 SAFETY ENDPOINTS

The primary endpoint is the number of adverse events recorded during the on-treatment period through visit 15. No formal statistical analysis will be made for the primary outcome. The primary endpoint will be presented by treatment groups in a summary table including number of AEs, number of subjects with at least 1 AE and percentage of exposed subjects with at least 1 AE. Placebo will be pooled across cohorts for comparison. AEs will also be summarized by system organ class, preferred term, seriousness, severity, outcome, and relationship to IMP using descriptive statistics.

Adverse events will be summarized over the entire trial (i.e., on-treatment and follow-up period). (i.e., visit 0 through visit 17 at 12 months). They will be further summarized by whether they occurred up to and including visit 6 (4 weeks) or later. Follow-up visits 16 and 17 will be conducted to obtain 6- and 12-month data on participants' metabolic status and reportable adverse event assessments.

All AEs will be coded using the CTCAE and mapped to latest version of Medical Dictionary for Regulatory Activities (MedDRA). AEs will be summarized by system organ class, preferred term, seriousness, severity, outcome, and relationship to IMP using descriptive statistics.

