8.2.2 SAFETY ANALYSES

Safety data will be analyzed in the SA population. Adverse events and select laboratory values (e.g., hematology, blood chemistry and others) may also be summarized by the treatment arms. Only grade 2 or higher AEs are to be reported for visits 16 and 17, as per protocol.

On-Treatment Adverse Events

An overall summary of AEs as described above will be provided. AEs will be summarized for all doses and also by dose. The most commonly reported AEs (5% or more of patients) will also be summarized by preferred term. A summary of AEs by preferred term and maximum CTCAE grade, as well the grouped maximum CTCAE grade group (Grade 1-2 vs. Grade 3-4 vs. Grade 5) will be presented. Only patients who experience AEs during the AE reporting period will be listed.

Treatment Related Adverse Events

Treatment-related AEs are those judged by the Investigator to be at least possibly related to the study drugs [with a cause related to study drug as indicated on the case report form (CRF)] or for which relatedness is recorded as "unknown" by the Investigator. Similar summaries as noted for AEs will be provided for treatment related AEs.

Serious Adverse Events and Death

On-treatment SAEs and treatment-related SAEs will be summarized by MedDRA SOC and preferred term. Patients who experienced a SAE during the SAE reporting period will be listed for all randomized patients. The number and percentage of patients who experienced any serious treatment - emergent SAE will be summarized for all doses. A summary of SAEs by preferred term, maximum CTCAE grade and grade group will be presented.

Deaths will be summarized by time period (on-treatment vs. during follow-up) and cause of death. Deaths that occurred on or after first dose of study medication and within 28 days after the last dose of study medication are defined as on-treatment deaths. A listing of death data will also be provided and it will include all deaths that occurred during the reporting period for deaths which starts from the signing of the informed consent to the end of the follow up period for death.

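### The primary AE count stays open about 43 days after the last dose following a full course but 35 days after any missed injection, and no person-time is reported beside it

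*Protocol*

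**What the plan says.** Protocol section 8 and SAP section 3 define the on-treatment period in the same words: from first treatment "through visit 15 (or 5 weeks after last treatment for subjects not receiving all injections"). SAP 6.1 builds the primary endpoint on that term: "The primary endpoint is the number of adverse events recorded during the on-treatment period through visit 15". The primary table, in Protocol 8.1 and again in SAP 6.1, gives "number of AEs, number of subjects with at least 1 AE and percentage of exposed subjects with at least 1 AE". Neither document plans person-time or event rates beside these counts.

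SAP 8.2.2 uses a different cutoff for deaths: those on or after first dose and "within 28 days after the last dose of study medication are defined as on-treatment deaths".

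The Schedule of Assessments puts dose 12 at visit 13, day 77, and visit 15 at day 120. Protocol 5.5 says "visit 15 should be within -3/+3 days from the target date", and the Schedule agrees. The plasmid DNA/RNA sampling lists in Protocol 8.3 and SAP 6.2 print "Visit 15, day 120 +/- 14 days; Visit 16, day 180 +/- 14 days".

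Grade 1 events are collected only up to visit 15; Protocol 7.1.1 states "After visit 15 only grade two or higher AEs are to be recorded".

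**The concern.** A raw count and a percentage with at least one event can be compared across dose groups only if people are observed for similar lengths of time, or if the difference in time is shown. Here the observation time depends on dosing status.

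This will arise in ordinary conduct. Protocol 4.4.2 withholds a dose for fever or active infection. Protocol 5.6 ends treatment only after two consecutive missed doses or more than two in total, so a person can miss one mid-course dose and still be dosed on day 77. A COVID-19 vaccination or booster during treatment also ends dosing. If stopping differs between dose groups, the group with more stopping contributes less time and, other things equal, shows fewer events. With nine active participants per cohort, one person more or less with an event moves the percentage by 1/9, about 11 points.

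The death cutoff raises a separate question of consistency: the same fatal event can be classed differently in two tables of one report.

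**Working it through.** **Inputs.** Dose d is given on day 7(d-1), so dose 12 is on day 77 (Schedule). Visit 15 is day 120 +/-3 (Protocol 5.5, Schedule). The alternative close is 5 weeks = 35 days (Protocol 8, SAP 3). The death cutoff is 28 days (SAP 8.2.2). Each cohort has nine active participants. The plan states no figure of its own to reproduce here.

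**Closing day.** Full course: visit 15. Otherwise: last dose day + 35.

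| Participant | Last dose (day) | Window closes (day) | Days after last dose |
|---|---|---|---|
| All 12 injections | 77 | 120 (117-123) | 43 (40-46) |
| One earlier dose missed, dosed on day 77 | 77 | 77+35 = 112 | 35 |
| Stops after dose 11 | 70 | 105 | 35 |
| Stops after dose 10 | 63 | 98 | 35 |
| Stops after dose 9 | 56 | 91 | 35 |
| Stops after dose 5 | 28 | 63 | 35 |
| Stops after dose 2 | 7 | 42 | 35 |

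Adding the +/-1 day dosing window widens 40-46 to 39-47. The first two rows share a last-dose day and close 120-112 = 8 days apart.

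**Person-days in an active arm of nine.**
- All full course: 9 x 120 = 1,080.
- Two stop after dose 5: 7 x 120 + 2 x 63 = 966, a shortfall of 114/1,080 = 10.6%.
- Two stop after dose 2: 840 + 84 = 924 (-14.4%). Two stop after dose 9: 840 + 182 = 1,022 (-5.4%).

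**What a rate would show.** The documents give no AE rate. Assume a constant 1 AE per 120 days (range 0.5 to 2). Expected counts are then 1,080/120 = 9.0 and 966/120 = 8.05 (4.5 and 4.0 at 0.5; 18 and 16.1 at 2). The rate is 100/120 = 0.83 per 100 person-days in both cases. The count moves although the underlying risk has not.

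**Would a common cutoff remove the shortfall?** With 35 days for everyone, a full course gives 9 x 112 = 1,008. Two dose-5 stoppers give 7 x 112 + 2 x 63 = 910, a shortfall of 98/1,008 = 9.7%. A common cutoff removes the 8-day gap and leaves almost all of the early-stopper shortfall.

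**Deaths.** After a full course the death cutoff is 77+28 = day 105, while the AE window runs to day 120. A fatal event on any of days 106-120 (15 days) is an on-treatment AE and a follow-up death.

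**The case against.** The strongest reply is that the plan is descriptive and already contains much of the remedy. SAP 6.1 plans no formal analysis of the primary outcome, and the same window rule applies to every arm. SAP 5.4 analyses people with at least 10 doses and, separately, everyone else. SAP 6.1 also summarises AEs over the whole trial and by before or after visit 6. SAP 8.2.1 reports doses given. Every death is listed from consent to the end of follow-up, and Protocol 8.1 summarises SAEs over the whole trial, so no death or SAE is lost. Closing a safety window a set time after the last dose is also sensible in itself.

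Most of this stands and limits the size of the point. It does not remove it. The at-least-10-dose group still mixes people with 10 or 11 doses (closing as early as day 98 or 105) with full-course participants (day 120), and none of these tables shows time at risk.

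Several stronger readings are tempting, but the documents do not support them:
- **That the window has no fixed close.** Visit 15 has a target, day 120, and a +/-3 day window. The week-16 label (16 x 7 = day 112) is no rival date: the same row puts day 180 under week 24 (day 168), so the row is approximate.
- **That the AE window spans 29 to 57 days** (106-77 to 134-77). The +/-14 days appears only in plasmid-sampling lists and is not stated as an AE window.
- **That SAP 6.1 contradicts SAP 3.** SAP 6.1 omits the 5-week clause but uses the term that SAP 3 defines with it.
- **That the COVID-19 rule lengthens the window.** Protocol 4.5 asks for 14 symptom-free days before visit 15. It gives no rescheduling rule and no extension of AE counting, so any deferral is an inference.
- **That 28 days is part of the primary endpoint.** It classifies deaths only.

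**Conclusion.** The point holds, at minor severity. The primary AE table will report raw counts and percentages over observation times that depend on dosing status, with no person-time to reveal it. The difference is 8 days for two people with the same day-77 last dose. It is much larger for early stoppers: about 11% of an arm's person-days if two of nine stop after dose 5, and 5% to 14% if they stop after dose 9 or dose 2. The death cutoff leaves a 15-day span after a full course in which one event carries two labels. The visit 15 window is printed two ways.

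The day arithmetic follows from the documents. The number of stoppers is illustrative, and the expected counts rest on an assumed constant AE rate. It is also assumed that a missed dose is not made up later, since no such provision is given. No loss of recorded data or safety follow-up is shown, and no test or power is affected.

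**What to change.** 1. **Show the time at risk.** Beside the primary counts, report person-days in the on-treatment window and AEs per 100 person-days by arm. This is the most useful change, because it shows the early-stopper shortfall that a common cutoff would leave. It is an added SAP table.
2. **Use one cutoff.** Count AEs with onset from first dose to 35 days after the last dose given, for everyone, and use the same 35 days for on-treatment deaths in SAP 8.2.2. A last dose on day 77 +/-1 then closes on days 111-113, before the earliest in-window visit 15 (day 117), so grade 1 recording covers the whole window. Add a supportive table through day 120 for all participants, noting that a visit 15 on days 117-119 ends grade 1 recording slightly earlier.
3. **Align the text.** Print visit 15 as +/-3 days in Protocol 8.3 and SAP 6.2, and repeat the SAP 3 definition in SAP 6.1.

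No new visit or sample is needed. The downside of item 2 is that AEs starting on days 113-120 after a full course (8/120 = 6.7% of the window) move from the primary to the supportive table. Items 2 and 3 change Protocol text, and Protocol 9.1 requires ethics approval before an amendment is implemented. Protocol 8.1 requires the SAP to be final before unblinding, and the documents do not show whether that has happened. If it has, keep the defined window and add the person-day and day-120 tables as deviations described in the study report, as SAP section 2 provides.
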